#### **4.3 Toxities and Dosing Delays/Dose Modifications**

Any patient who receives treatment on this protocol will be evaluable for toxicity. Each patient will be assessed periodically for the development of any toxicity

according to the Time and Events table ([Section 5.1](#)). Toxicity will be assessed according to the NCI Common Toxicity Criteria for Adverse Events (CTCAE) Version 4.0 and the RTOG Late Radiation Morbidity Score ([See Appendix F](#)).

### **Radiation Adverse Events**

**Table 3: Non-hematological Toxicity: Modifications for Recurrent Toxicity**

| NCI CTCAE Version 4 Grade               | Conformal Radiotherapy  |
|---|---|
| 0-2                                     | No change from original starting dose                         |
| 3                                       | Hold until resolved to $\leq$ Grade 2, then resume treatment. |
| Second episode of grade 3 or 4 toxicity | Hold until resolved to $\leq$ Grade 2, then resume treatment. |
| Third episode of grade 3 or 4 toxicity  | Remove subject from trial                                     |

**Table 4: Non-hematological Toxicities: Modifications for Various Expected Toxicities**

| Non-hematological Toxicity Dose Reductions for Conformal Radiotherapy |   |
|---|---|
| Event   | Action  |
| Nausea   |   |
| Grade 1-2   | None  |
| Grade 3   | Hold until resolved to $\leq$ Grade 2, then resume treatment. |
| Grade 4   | Hold until resolved to $\leq$ Grade 2, then resume treatment. |
| Vomiting   |   |
| Grade 1-2   | None  |
| Grade 3   | Hold until resolved to $\leq$ Grade 2, then resume treatment. |
| Grade 4   | Hold until resolved to $\leq$ Grade 2, then resume treatment. |
| Mucositis  |   |
| Grade 1-2   | None  |
| Grade 3   | Hold until resolved to $\leq$ Grade 2, then resume treatment. |
| Grade 4   | Hold until resolved to $\leq$ Grade 2, then resume treatment. |
| Esophagitis  |   |
| Grade 1-2   | None  |
| Grade 3   | Hold until resolved to $\leq$ Grade 2, then resume treatment. |
| Grade 4   | Hold until resolved to $\leq$ Grade 2, then resume treatment. |
| Fatigue  |   |
| Grade 1-2   | None  |
| Grade 3   | Hold until resolved to $\leq$ Grade 2, then resume treatment. |
| Grade 4   | Hold until resolved to $\leq$ Grade 2, then resume treatment. |
| Dermatitis   |   |
| Grade 1-2   | None  |
| Grade 3   | Hold until resolved to $\leq$ Grade 2, then resume treatment. |
| Grade 4   | Hold until resolved to $\leq$ Grade 2, then resume treatment. |

#### **4.4 Concomitant Medications/Treatments**

Not applicable.

#### **4.5 Other Modalities or Procedures**

Not applicable.

#### **4.6 Duration of Therapy**

In the absence of treatment delays due to adverse events, treatment may continue for 2 to 5 fractions depending of the clinical situation. We expect most patients to receive treatments for less than 1 week, however, all treatments will be completed within 21 days. Receiving treatment for > 21 days will be a major protocol violation. Remaining fractions will be discontinued if:

- Inter-current illness that prevent further administration of treatment
- Unacceptable adverse events
- The patient decides to withdraw from the study, OR
- General or specific changes in the patient's condition render the patient unacceptable for further treatment in the judgment of the investigator.

#### **4.7 Duration of Follow Up**

After removal from study, patients will be followed for 12 months after treatment was initiated or until death, whichever occurs first. Patients removed from study for treatment-related adverse events will be followed until resolution or stabilization of the adverse event.

#### **4.8 Pregnancy**

Women of childbearing potential (WOCBP) includes any female who has experienced menarche and who has not undergone successful surgical sterilization (hysterectomy, bilateral tubal ligation or bilateral oophorectomy) or is not postmenopausal [defined as amenorrhea  $\geq$  12 consecutive months; or women on hormone replacement therapy (HRT) with documented serum follicle stimulating hormone (FSH) level  $> 35$  mIU/mL]. Even women who are using oral, implanted or injectable contraceptive hormones or mechanical products such as an intrauterine device or barrier methods (diaphragm, condoms, spermicides) to prevent pregnancy or practicing abstinence or where partner is sterile (e.g., vasectomy), should be considered to be of child bearing potential.

WOCBP must have a negative serum or urine pregnancy test (minimum sensitivity 25 IU/L or equivalent units of HCG, or in accordance with local regulations, whichever is more sensitive) within 7 days prior to the start of study treatment or in accordance with local regulations, whichever is of shorter duration.

Prior to study enrollment, WOCBP must be advised of the importance of avoiding pregnancy during trial participation and the potential risk factors for an unintentional pregnancy.

All WOCBP MUST have a negative pregnancy test within 7 days prior to first receiving study treatment. If the pregnancy test is positive, the patient must not receive investigational product and must not be enrolled in the study.

**In addition, all WOCBP should be instructed to contact the Investigator immediately if they suspect they might be pregnant (e.g., missed or late menstrual period) at any time during study participation.**

Male subjects who are actively trying to conceive will be counseled to wait for 6 months following radiation therapy to allow spermatogenesis to recover.

#### **4.9 Removal of Patients from Protocol Therapy**

Patients will be removed from study when any of the criteria listed in Section 4.6 apply. Notify the Principal Investigator, and document the reason for study removal and the date the patient was removed in the Case Report Form. The patient should be followed-up per protocol.

#### **4.10 Expected Adverse Events**

Depending on the site of treatment, potential / expected treatment toxicities include Grade 1 to 3 toxicity of the following symptoms, with Grade 3 occurring in no more than the following percentages of patients:

|             |     |
|-------------|-----|
| Dermatitis  | 20% |
| Nausea      | 20% |
| Fatigue     | 20% |
| Vomiting    | 20% |
| Diarrhea    | 20% |
| Mucositis   | 20% |
| Esophagitis | 20% |

## **5.0 EVALUATIONS AND ASSESSMENTS**

### **5.1 Time and Events Table**

|  | Pre-treatment | During treatment | Week 1 | Week 4 | Week 8 | Week 12 | 6-Month | 12-Month |
|--|----------------------|-------------------------|---------------|---------------|---------------|----------------|----------------|-----------------|
| Informed Consent                                   | X                    |                         |               |               |               |                |                |                 |
| History and PE                                     | X                    |                         |               | X             |               | X              | X              | X               |
| Karnofsky Performance Status                       | X                    |                         | X             | X             | X             | X              | X              | X               |
| Toxicity Evaluations                               |                      | X                       | X             | X             | X             | X              | X              | X               |
| Opiod Logbook Evaluation                           | X                    | X                       | X             | X             | X             | X              |                |                 |
| Brief Pain Inventory                               | X                    |                         | X             | X             | X             | X              | X              | X               |
| FACT-BP and FACT-G surveys                         | X                    |                         | X             | X             | X             | X              | X              | X               |
| Satisfaction and Convenience Survey                | X                    |                         | X             | X             | X             | X              | X              | X               |
| Quality Assurance                                  | X                    |                         |               |               |               |                |                |                 |
| Diagnostic Imaging (CT/MRI/PET CT)                 | X                    |                         |               |               |               |                |                |                 |
| Pathology  | X                    |                         |               |               |               |                |                |                 |
| Pregnancy test (< 7 days)                          | X                    |                         |               |               |               |                |                |                 |
| Radiotherapy Delivery                              |                      | X                       |               |               |               |                |                |                 |
| Exit Radiation Dose Verification                   |                      | X                       |               |               |               |                |                |                 |
| Intrafractional Motion Monitoring                  |                      | X                       |               |               |               |                |                |                 |
| Conventional and Expedited Image Registration Flow |                      | X                       |               |               |               |                |                |                 |

### **5.2 Correlative Studies Procedures**

Not applicable.

### **5.3 Final Study Visit**

The final study visit will occur at the 12 month visit. See the Time and Events Table for assessments that will be performed. Patients removed from study for treatment-related adverse events will be followed until resolution or stabilization of the adverse event

### **5.4 Early Termination Visit**

Subjects may withdraw voluntarily from participation in the study at any time. At the time of withdrawal, the subject will be requested to provide their opioid logbook and complete the following surveys: BPI, FACT-BP/FACT-G, and Satisfaction survey.

Subjects may also withdraw voluntarily from receiving the study intervention for any reason. If that is the case, they will be encouraged to continue regular follow-up evaluations according to the Time and Events table.

As all of these patients have metastatic cancer and a limited life expectancy, it is likely that a reasonable percentage of study participants will choose hospice care before the completion of their follow-up.

## **6.0 EVALUATION CRITERIA**

### **6.1 Response to Palliative Radiotherapy**

#### **6.1.1 Response Criteria According to the International Bone Metastases Consensus Group**

Complete Response (CR): Pain reduction to zero AND OMED\* stable or reduced

Partial Response (PR): Pain reduction by two scores or more AND OMED\* stable or reduced.  
OR  
Stable pain AND OMED\* reduction by 25% or more

Pain Progression (PP): Pain increase by two scores or more AND OMED\* stable or increased.  
OR  
No change in pain AND OMED\* increased by 25% or more (or start of morphine use after the baseline or epidural pain treatment at follow-up)

Stable Pain (SP): Stable pain AND stable OMED\*

OMED = Oral Morphine Equivalent Dose

\* The total OMED intake over the most recent 72 hours will be calculated at each evaluation.

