## **3.0 PATIENT ELIGIBILITY**

### **3.1 Inclusion Criteria**

- 3.1.1** Patient has a biopsy proven diagnosis of cancer. The osseous metastatic lesions do not need to be biopsied.
- 3.1.2** Patients with multiple myeloma are eligible for the study.
- 3.1.3** Patient has 1-3 major painful osseous metastases (target lesions) from any primary cancer or unknown primary cancer.
- 3.1.4** Long bone target lesions must have a Mirels fracture score of  $\leq 7$  (See Appendix G).
- 3.1.5** Radiation oncologist determines that the patient is medically able to undergo palliative radiation therapy.
- 3.1.6** Patient has target lesions that are radiographically consistent with metastatic disease on CT, MR, or PET CT obtained within 8 weeks of treatment.
- 3.1.7** Persistent distinguishable pain associated with target sites to be treated.
- 3.1.8** Patient average BPI pain score for last 72 hours at specified location is  $\geq 3$  (0-10 scale)
- 3.1.9** Patients may have additional non-painful or minimally painful osseous metastases (if patient has pain from additional sites, the pain from the additional sites must be evaluated as being less intense by at least 2 points on the BPI compared to the site(s) treated)
- 3.1.10** The patient may have previously been treated with external beam radiation therapy to other body sites, but not to the target sites.
- 3.1.11** The patient may have previously or currently be undergoing chemotherapy or bisphosphonate therapy.

- 3.1.12** The patient will be able to understand English (or a medical interpreter for their native language must be available for all study visits).
- 3.1.13** 18 years of age or older.
- 3.1.14** Life expectancy > 12 weeks.
- 3.1.15** Able and willing to answer simple survey questionnaires.
- 3.1.16** Able and willing to keep a logbook of analgesic use (with or without assistance)
- 3.1.17** Willing to return to clinic at 4 weeks, 12 weeks, 6 months, and 12 months after treatment.
- 3.1.18** Signed study-specific informed consent form.
- 3.1.19** Women of childbearing potential and men must agree to use adequate contraception (hormonal or barrier method of birth control) prior to study entry and for the duration of study participation. Should a woman become pregnant or suspect she is pregnant while participating in this study, she should inform her treating physician immediately.

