## **3.2 Exclusion Criteria**

- 3.2.1** Inability to lie flat on table for treatment
- 3.2.2** Patient with  $\leq$  12 weeks life expectancy
- 3.2.3** Systemic therapeutic radionuclide delivery within 30 days prior to treatment
- 3.2.4** Epidural compression of spinal cord or cauda equine
- 3.2.5** Long bone target lesions must have a Mirels fracture score of  $\leq$  7
- 3.2.6** Spinal canal compromise > 25%
- 3.2.7** Unstable spine requiring surgical stabilization

**3.2.8** Target lesions have previously been treated with external beam radiation.

**3.2.9** PTV located within 5mm of spinal cord or cauda equina.

**3.2.10** A serious uncontrolled medical disorder that, in the opinion of the Investigator, would impair the ability of the patient to receive protocol therapy.

**3.2.11** Pregnant and breastfeeding women are excluded from this study.

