### **6.1.2 Duration of Response**

Duration of overall response: The duration of overall response is measured from the time measurement criteria are met for Complete Response or Partial Response (whichever is first recorded) until the first date that Stable Pain or Pain Progression is objectively documented.

The duration of overall CR is measured from the time measurement criteria are first met for CR until the first date that Partial Response is objectively documented.

Duration of stable pain: Stable Pain is measured from the start of the treatment until the criteria for Pain Progression are met, taking as reference the baseline measurements recorded just prior to treatment.

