### **7.3 Data Analyses Plans**

Treatment response as defined by International Bone Metastases Consensus Group will be determined for each patient. As described in Section 6.1.1, pain intensity as defined by the BPI and opiate use as quantified by the OMED will be used to categorize patients as having: Complete Response, Partial Response, Pain Progression, Stable Pain. At each evaluation, the patient's BPI and OMED at that visit will be compared to the pre-treatment levels. The "Worst Pain" score from the patient's BPI will be used to evaluate for treatment response. Patient response does not require a statistical analysis. The percentage of patients in each response category at each evaluation will be reported.

Patient pain will be recorded using the BPI before treatment and at designated evaluations after treatment. Pain scores before and after treatment will be compared using a Wilcoxon signed ranks test to determine if there is a statistically significant difference. Example: Pre-treatment vs. 1 week, Pre-treatment vs. 4 weeks, etc.

Analgesic use will be recorded by requiring each patient to keep a logbook of their analgesic intake. Their opiate intake for the last 72 hours will be converted to OMED at each evaluation and used in the categorization of treatment response. The difference between their OMED before and after treatment will be compared using paired two-sample t-tests.

Patients' functional status will be determined using the Karnofsky Performance Scale at each evaluation. The difference between the KPS before and after treatment will be compared using a Wilcoxon signed ranks test.

Patients' quality of life will be measured using FACT-BP and FACT-G scores at each evaluation. The difference between the FACT scores before and after treatment will be compared using a Wilcoxon signed ranks test.

Patient satisfaction will be measured using a modified version of FACT - TS – BTCSQ. No statistical analysis will be required for reporting the results. The average scores from the satisfaction survey will be reported.

To evaluate the CT detector dose calculations, the delivered radiation dose obtained using the phantom quality assurance will be compared to the exit radiation dose quality assurance calculation. The calculated dose and delivered dose for each patient will be compared using a paired two-sample t-test, and the % difference in dose will be reported.

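### As written, the response rules credit STAT RT with pain relief that follows an epidural or other non-opioid treatment of a target site

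*Combined protocol and SAP*

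**What the plan says.** Section 6.1.1 defines four categories from pain and OMED. Complete Response (CR) needs zero pain with OMED stable or reduced. The first limb of Partial Response (PR) begins "Pain reduction by two scores or more AND OMED" and carries the same OMED condition. The second limb is stable pain with an OMED fall of 25% or more. The second limb of Pain Progression (PP) begins "No change in pain AND OMED", requires an OMED rise of 25% or more, and adds in parenthesis "or start of morphine use after the baseline or epidural pain treatment at follow-up". Stable Pain (SP) is stable pain with stable OMED. No category mentions any other treatment.

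Section 7.3 scores each visit from these two quantities alone: "At each evaluation, the patient's BPI and OMED at that visit will be compared to the pre-treatment levels". Section 6.1.2 measures overall response "until the first date that Stable Pain or Pain Progression is objectively documented".

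Sections 4.4 (concomitant treatments) and 4.5 (other modalities) each read "Not applicable". Inclusion criterion 3.1.11 says: "The patient may have previously or currently be undergoing chemotherapy or bisphosphonate therapy". The Time and Events Table in 5.1 has no row for treatment given after STAT RT.

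**The concern.** Objective 2.1.1 is the response to STAT RT, and section 7.1 describes a non-randomized trial, so no control arm absorbs the effect of other treatment. A patient whose target site still hurts, or hurts again, may receive another local treatment. If it works, the next pain score is low. Unless the rules say otherwise, that low score is read as a response to STAT RT.

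The authors evidently saw the problem for epidurals, because they listed one as a sign of progression. Its position in the text makes it act only when pain has not changed, which is when the epidural has not helped. For other non-opioid local treatment there is no rule. Both the response percentage and the response duration are exposed.

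**Working it through.** **The plan's own figure.** The plan gives no figure for response. Its one computed figure is the 21 patients in section 7.2 (mean change 2, SD 3, two-sided alpha 0.05, power 80%). With d = 2/3, a paired t-test needs 20. Allowing for the Wilcoxon test's efficiency of 3/π under normality, 21 gives power 0.808. The figure is reproduced and does not depend on response scoring. Below, 21 and the planned 30 serve only as denominators.

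**Applying 6.1.1.** Inputs: baseline pain 7 (illustrative), pain changes from −7 to +2, and OMED changes of −50%, 0 and +50%. Conventions that 6.1.1 does not spell out: no change in pain means exactly 0, stable pain means a change of less than 2, and stable OMED means a change of less than 25%. Each cell shows the category without an epidural, then with one.

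| Pain change | OMED −50% | OMED 0% | OMED +50% |
|---|---|---|---|
| −7 (to zero) | CR; CR | CR; CR | none; none |
| −4 or −2 | PR; PR | PR; PR | none; none |
| −1 | PR; PR | SP; SP | none; none |
| 0 | PR; PR and PP | SP; SP and PP | PP; PP |
| +1 | PR; PR | SP; SP | none; none |
| +2 | none; none | PP; PP | PP; PP |

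- At a fall of 2 or more the epidural never changes the category.
- It matters only in the row for unchanged pain. There it adds PP to PR or to SP, and the text does not say which prevails.
- The start-of-morphine trigger has the same overlap. A patient moved from another opioid to morphine at the same OMED, with pain unchanged, meets both SP and PP.
- If no change is read as within 1 point, the −1 and +1 rows also gain the overlap. The rows for a fall of 2 or more stay as they are.
- If the parenthesis is read as a stand-alone trigger, an epidural followed by a fall of 2 or more meets PP and PR (or CR) together, again without precedence.

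**Duration.** Under 6.1.2 a response ends only when SP or PP is documented. If pain returns and is treated between visits, for example between week 12 and 6 months, and the next visit again scores PR, duration runs on. If the first CR or PR follows the second treatment, the clock starts there. If SP or PP is documented at a visit before the second treatment, duration has already ended.

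**What is recorded.**

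- Item 7 of the Brief Pain Inventory (BPI, Appendix H) asks what pain treatments the patient receives, at every BPI visit through 12 months. It asks for neither target site nor start date.
- Logbook evaluation is scheduled to week 12 and is blank at 6 and 12 months.
- History and physical examination is scheduled at weeks 4 and 12 and at 6 and 12 months.
- Appendix E counts hospital and outpatient visits, not what was done at them.
- Under 8.1.1, adverse events are collected to 30 days after the last treatment.

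**Size.** If k patients would otherwise be non-responders, receive such treatment and then meet CR or PR, the response rate rises by k/n. One patient adds 1/30 = 3.3 points, or 1/21 = 4.8 points if only 21 are evaluable. The documents give no value for k.

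**The case against.** The strongest reply is that the rules already contain protection. CR and the pain-fall limb of PR require OMED stable or reduced, so opioid rescue that raises OMED by 25% or more is not a response. This stands, and it confines the point to epidurals and non-opioid treatment. The protection is less certain at 6 and 12 months, where no logbook evaluation is scheduled although 6.1.1 calls for OMED at each evaluation. Whether an epidural opioid enters OMED is not stated.

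A reader might infer that later treatment is not recorded at all. The documents do not support that: BPI item 7, the logbook, and history and examination each capture part of it. What is missing is systematic capture by site and start date, and any use in scoring.

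A reader might also infer that the bias always favours STAT RT. That is not shown. Opioid rescue with falling pain fits no category, an epidural at unchanged pain can count as progression, and retreating a patient who is already responding does not change that visit's category. Nor is every later systemic agent or radionuclide a sign of failure at the target site, since it may be given for disease elsewhere. The exclusion "Systemic therapeutic radionuclide delivery within 30 days prior to treatment" is an eligibility washout and does not imply a scoring rule for follow-up.

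Finally, scoring retreated patients as non-responders departs from the consensus categories that objective 2.1.1 adopts, and other strategies are defensible. This is a fair reason to report response both ways. It does not excuse leaving the handling unstated. Response is reported descriptively, and one patient is small beside sampling error (18/30 = 60% has an exact 95% interval of 41 to 77%), but an interval does not correct a misassigned category.

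**Conclusion.** The point holds in a limited form. Followed exactly, 6.1.1 scores a patient as PR or CR when pain falls enough after an epidural and OMED is stable or reduced. The same applies after repeat radiation, surgery, ablation or a nerve block at a target site. At unchanged pain, the epidural and morphine triggers put one patient in two categories. Section 6.1.2 can credit STAT RT with relief maintained by a second treatment.

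The size is 3.3 points for each affected patient with 30 evaluable, provided that the patient would otherwise be a non-responder. It is tempting to assume a count: six such patients would add 6/30 = 20 points, the gap between the protocol's benchmarks of about 60% and over 80%. Nothing in the documents supports any particular count, and the plan makes no formal test against either benchmark, so the total effect is unknown. The sample size is unaffected.

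**What to change.** These changes concern endpoint scoring and recording only. They restrict no treatment.

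1. In 6.1.1, take the epidural clause out of the unchanged-pain limb and state a precedence among the categories, covering the start-of-morphine trigger too. After an epidural or other pain-directed local treatment of a target site, the patient is not counted as CR or PR to STAT RT at later visits in the main summary. State how this applies when only one of several targets is retreated.
2. In 6.1.2, end response duration at the date of that treatment.
3. In 4.4, 4.5 and the Time and Events Table, require the type, site and date of such treatments to be recorded at the scheduled visits through 12 months. Do the same for any start or change of systemic, radionuclide or bone-modifying therapy.
4. In 7.3, add a sensitivity analysis of response regardless of later treatment. Describe, without excluding, patients who started new systemic or radionuclide therapy.

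The cost is protocol wording, one case report form line at visits already scheduled, and a possibly lower reported response rate and duration.
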